At the first visit, the Investigator will discuss with the subject the various treatment alternatives for a Breast Ptosis, both non-surgical and surgical, including the minimally invasive RF and other treatment modalities.

VISIT 1:

SCREENING

During the first visit, the investigator or a representative on his behalf will obtain an Informed Consent Form (ICF) from the subject, clearly indicating his/her understanding of the requirements and risks involved with study participation.

Possible adverse effects include but not limited to bleeding, infection, scarring, skin contour irregularities, thermal trauma to the skin, asymmetry, scarring, surgical shock, pulmonary complications, skin loss, seroma, allergic reaction, and anesthesia related complications can occur and should be discussed and understood. The subject must understand the importance of pre-treatment and

	Clinical Evaluation of Safety and Efficacy of Radio-Frequency Assisted Lipolysis (RFAL) of Breast Envelope and Nipple-Areolar Complex (NAC) Position	
	Protocol No: DO607738A SIRB ID: 6254	Rev. Date: August, 2018

post-treatment instructions and that failure to comply with these instructions may increase the probability of complications.

The Investigator will obtain a focused subject medical history including exclusion criteria specified herein and the front, back and both sides of the treatment area using a high resolution digital camera, as well as additional information that is specified in the case report form.

The follow-up visits should be scheduled 1 week, 6 weeks, 3 months, 6 months and optional 12 months after the treatment.

Photographs should be taken prior to the baseline treatment and at each of the follow-up visits, as well as Vectra 3D Imaging and static measurements. Participants must have a recorded mammogram prior to the first treatment. All measurements will be recorded on the case report form (CRF).

VISIT 2:

TREATMENT

The treatment will be performed once. The treatment procedure should be conducted according to the following guidelines:

INMODE
aesthetic solutions

Clinical Evaluation of Safety and Efficacy of Radio-Frequency Assisted Lipolysis (RFAL) of Breast Envelope and Nipple-Areolar Complex (NAC) Position

Protocol No:
DO607738A

Rev. Date: August, 2018

SIRB ID: 6254

Treatment Parameters

Treatment area	Treatment depth	Hand Piece	External Cut-off Temperature	Internal Cut-off Temperature	Treatment time

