- Sternal Notch to Nipple
- Nipple to IMF
- Base Width (at point of breast take off from chest wall)

INMODE
aesthetic solutions

[figure not shown]
Clinical Evaluation of Safety and Efficacy of Radio-Frequency Assisted Lipolysis (RFAL) of Breast Envelope and Nipple-Areolar Complex (NAC) Position

Protocol No:
DO607738A

Rev. Date: August, 2018

SIRB ID: 6254

- Nipple to nipple.

1. Base width (BW)
2. Nipple to inframammary fold distance (N-IMF)
3. Intermammary distance
4. Sternal notch to nipple distance (SN-N)
5. Soft tissue pinch test (PT)
6. Maximum skin stretch (MSS)

EVALUATION

Three independent plastic surgeons will evaluate photographs of the preoperative and postoperative photographs at 3-, 6- and if applicable, 12-month results.

DISCONTINUATION

Subjects enrolled in the study will be free to discontinue their participation in the study at any time. A decision to discontinue participation will not prejudice their medical care. In those instances, Investigators will attempt to obtain clinical results and side effect evaluation concerning the subject prior to his/ her withdrawal.

INMODE
aesthetic solutions

Clinical Evaluation of Safety and Efficacy of Radio-Frequency Assisted Lipolysis (RFAL) of Breast Envelope and Nipple-Areolar Complex (NAC) Position

Protocol No:
DO607738A

Rev. Date: August, 2018

SIRB ID: 6254

DATA ANALYSIS

Statistical analysis of all major body factors will be performed to determine quantitatively the treatment efficacy.

The data will be analysed by the Sponsor using basic descriptive statistics, as well as comparison tests, where applicable. Treatment-related complications will be monitored and reported; if applicable, their incidence rate will be calculated and analysed for any relationship to treatment parameters and/or skin type.

RISK/BENEFIT ANALYSIS

RISKS

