Anticipated adverse events in this study include: pain, excessive skin redness (erythema), damage to natural skin texture (scratching, crusting, blister and burn), bleeding, bruising, infection, scarring, skin contour irregularities and/or asymmetry, pulmonary complications, complications following reaction to surgery and/or to anesthesia. There are also specific anticipated adverse events that may occur due to the punch biopsy procedure: complications following reaction to the anesthesia, infection and scarring. If an *unanticipated* adverse event occurs at any time during or after the use of the InModeRF system, the Physician must report it to the Sponsor. If the unanticipated adverse event, in the opinion of the Sponsor or the Physician, is likely to affect the safety of the subjects or the conduct of the study, the IRB will be notified of the effect within 10 working days after the Sponsor first receives notice of it.

	Clinical Evaluation of Safety and Efficacy of Radio-Frequency Assisted Lipolysis (RFAL) of Breast Envelope and Nipple-Areolar Complex (NAC) Position	
	Protocol No: DO607738A SIRB ID: 6254	Rev. Date: August, 2018

COST TO PARTICIPANTS

There is no cost to subject for participation.

COMPENSATION TO PARTICIPANTS

Patients will be compensated \$100.00 for study completion (Last 12M FU).

COMPENSATION FOR RESEARCH RELATED INJURY

In the event of a research-related injury, the sponsor of the study will pay for reasonable costs of medical treatment, except for the costs covered by the patient's medical insurance. The Sponsor will not provide any other form of compensation.

RECORDS AND REPORTS

Data from the pre/post-treatment evaluations, the treatment sessions, complications, if any, and all follow-up evaluations will be recorded on the CRFs prepared for this clinical study.

Should a subject drop from the study prematurely, the Physician will attempt to obtain clinical results and side effects evaluation concerning the subject prior to his/her withdrawal. All specified records and reports concerning this study will be forwarded to the Sponsor within a reasonable period of time.

The participating Physicians shall retain all study-related documentation for a period of two years following the date on which the clinical investigation is terminated or discontinued.

I N M O D E
aesthetic solutions

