APPENDIX I
STUDY SCHEMATICS

	Visit 1 Pre Tx 1	Visit 2 Tx 1	Visit 3 1 W FU	Visit 4 6 W FU	Visit 5 3 M FU	Visit 6 6 M FU	Visit 7 12 M FU
Informed consent process	X						
Eligibility & medical history	X						
Final enrollment	X						
Mammogram	X						
CRF measurements: Weight, static measurements	X	X	X	X	X	X	X
Photography	X	X	X	X	X	X	X
3D Image	X	X	X	X	X	X	X
Treatment ^[1]	X						
Removal of stitches			X				
Physician assessment of results			X	X	X	X	X
Subject satisfaction			X	X	X	X	X
End of study							X

	Clinical Evaluation of Safety and Efficacy of Radio-Frequency Assisted Lipolysis (RFAL) of Breast Envelope and Nipple-Areolar Complex (NAC) Position	
	Protocol No: DO607738A SIRB ID: 6254	Rev. Date: August, 2018

^[1] It is important to document what kind of anesthesia was used during the treatment and if tumescent fluid was used as well which may influence the subject's sensation.

References

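### The efficacy analysis names no deciding measure and no deciding visit, so any of several measurements at any of four or five visits could be reported as efficacy

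*Combined protocol and SAP*

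**What the plan says.** The Study Objectives in the Protocol Synopsis name the Vectra 3D system as the tool for judging the breast envelope and the nipple-areolar position. They give no time point.

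Visit 1 (Screening) sets the timetable: "The follow-up visits should be scheduled 1 week, 6 weeks, 3 months, 6 months and optional 12 months after the treatment". It asks for photographs before treatment and "at each of the follow-up visits, as well as Vectra 3D Imaging and static measurements". Appendix I agrees: the rows for static measurements and for the 3D image are marked at every visit, including both Visit 1 and Visit 2. The Static Measurements section has four bulleted distances (sternal notch to nipple, nipple to inframammary fold, base width, nipple to nipple), followed by a numbered list of six items.

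The Data Analysis section then says: "Statistical analysis of all major body factors will be performed to determine quantitatively the treatment efficacy". On method it says: "The data will be analysed by the Sponsor using basic descriptive statistics, as well as comparison tests, where applicable". It names no primary measurement, visit, hypothesis or significance level.

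One section does restrict timing. Under Evaluation: "Three independent plastic surgeons will evaluate photographs of the preoperative and postoperative photographs at 3-, 6- and if applicable, 12-month results". That covers photographs only and does not say which of the three times decides.

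**The concern.** The plan intends more than description: it uses comparison tests to settle efficacy quantitatively. Several measurements at several visits are all eligible, and no rule set in advance says which one answers the question. If the choice is made after the data are seen, the most favourable measurement and visit can become the result, and its p-value no longer has its nominal meaning.

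This matters more here than in a controlled trial. The study is single-arm, open-label, limited to 10 women and analysed by the sponsor. Fixing the measurement and visit beforehand is one of the few protections available to it. The Device Description also lists durability of the correction as an open question, and a reading at 1 or 6 weeks cannot answer that.

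**Working it through.** The plan states no significance level, power, effect size or SD, so it has no figure to reproduce. The calculation below shows what the open choice could cost.

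**Inputs from the plan.** Up to 10 women (Scope and Duration of the Study); four required follow-up visits and one optional (Visit 1, Appendix I); four bulleted static distances (Static Measurements).

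**Assumptions.** Exactly 10 women with complete data; no true change in any measurement; a two-sided 5% one-sample t-test on each change from baseline; equal correlation between visits' changes of 0.5 or 0.8; correlation between distances of 0 or 0.5. A correlation of 0.5 between visits is what a shared baseline with equal, independent measurement error gives.

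**Step 1: independent tests as an upper reference.** The chance of at least one false positive in k tests is 1 − (1 − 0.05)^k.
- k = 4: 1 − 0.95^4 = 0.185
- k = 5: 1 − 0.95^5 = 0.226

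**Step 2: correlated visits, one measurement.** For each simulated study, draw 10 women's changes at k visits from a multivariate normal distribution with mean zero. Compute t = mean / (SD/√10) at each visit and count the study if any |t| exceeds 2.262 (the 97.5% point of t on 9 degrees of freedom). With 200,000 studies per cell:

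| Visits that may count | Correlation 0.5 | Correlation 0.8 |
|---|---|---|
| 1 (named in advance) | 0.050 | 0.050 |
| 2 (3 and 6 months) | 0.092 | 0.082 |
| 4 (all required) | 0.161 | 0.120 |
| 5 (with 12 months) | 0.190 | 0.135 |

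**Step 3: the measurement left open as well.** Four distances at four visits make 16 tests (100,000 studies).
- Between-visit 0.5, between-distance 0: 0.502
- Between-visit 0.8, between-distance 0.5: 0.351

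**Step 4: which open choice matters more.** Choosing among the four distances at one fixed visit gives about 0.16 (correlation 0.5) to 0.19 (independent). Choosing among the four visits for one fixed distance gives 0.12 to 0.16. The unnamed measurement therefore contributes at least as much as the unnamed visit, and naming only one of the two leaves a good part of the problem.

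**Step 5: what one named test can detect.** With 10 women the noncentrality is d√10, where d is the mean change in SD units.
- d = 1: noncentrality 3.16, power 0.803
- d = 0.75: noncentrality 2.37, power 0.562

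A single pre-named test is therefore still useful for a large change.

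**The case against.** The strongest reply is that this is a small single-arm pilot whose analysis is mainly descriptive, and that the significance level, the test and the correlations above are not in the plan. That is true of the inputs, so the percentages illustrate and do not measure. It does not remove the gap, because the plan itself calls for comparison tests to establish efficacy.

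A second reply is that the three surgeons' review starts at 3 months, so the plan already looks to later results. It does so for photographs. The rule does not extend to Vectra or static values, and it leaves three possible times.

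A reader might also infer two stronger points that the documents do not support.

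- *The early measurements are distorted by compression garments or swelling.* Post-Treatment Care makes garments optional, for up to 6 weeks, and no text has imaging done in a garment. Swelling is a listed risk with no stated duration. Nothing says that either alters the measured distances, and nothing makes an early visit decisive. The point stands without this.
- *The outcome timetables conflict.* Appendix I marks "Physician assessment of results" from week 1, while the three surgeons start at 3 months. These are different raters using different instruments: the visit descriptions have the patient and the physician complete forms at every follow-up, and the independent surgeons rate photographs. Different schedules for different instruments are not a contradiction.

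Finally, 6 months is a judgement. Follow-up can run to a year, and 12 months would say more about durability, but that visit is optional.

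**Conclusion.** The concern holds as a gap in pre-specification: efficacy is to be tested, but neither the measurement nor the visit that decides it is named. Under the stated assumptions, the false-positive chance is 12% to 16% across the four required visits for one measurement. It is 35% to 50% if the four bulleted distances are also open, against 5% for one named test. These figures depend on the assumed 5% level, the t-test and the correlations, and on counting four distances when the numbered list has six items. They assume no true change at any visit, so they say nothing about any effect of recovery on the readings. The point is modest in weight and is worth making because the remedy is cheap.

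**What to change.** Add to Data Analysis, before any follow-up data are analysed:

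> The primary efficacy measure is the change from Visit 1 (pre-treatment) to 6 months in sternal-notch-to-nipple distance, taken as the static measurement, or from Vectra in one fixed arm position if the sponsor so chooses before any follow-up data are analysed, averaged over the two breasts so that the woman is the unit of analysis. Per-breast values are also reported, and any left/right comparison of treatment parameters is separate and descriptive. All other measures, including those of the breast envelope, and the 3- and 12-month values are supportive; 1- and 6-week values describe recovery and are not tested for efficacy.

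Reasons for the details:
- Six months is the latest required visit and one of the surgeons' rating times.
- The baseline visit must be named because Appendix I has measurements at both Visit 1 and Visit 2.
- The arm position must be fixed if Vectra is used, because the Vectra section has scans taken with the arms in more than one position.
- Per-breast values are kept because the Treatment Parameters Study section lets the two sides be treated differently, and because correction of asymmetry is among the eligible indications; an average alone could hide change in either case.

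The cost is one paragraph, with no added visit, measurement or procedure. There are three downsides. A woman who misses 6 months has no primary value. An early, short-lived lift is described but not tested. The primary measure covers nipple-areolar position only, so the breast envelope, which the objective also names, is supportive.

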STUDY NAME: CLINICAL EVALUATION OF SAFETY AND EFFICACY OF RADIO-FREQUENCY ASSISTED LIPOLYSIS (RFAL) OF BREAST ENVELOPE AND NIPPLE-AREOLAR COMPLEX (NAC) POSITION

Date:

August 2018

Identifiers: NCT03863834 Unique Protocol ID: D0607738

I N M O D E
aesthetic solutions

Clinical Evaluation of Safety and Efficacy of Radio-Frequency Assisted Lipolysis (RFAL) of Breast Envelope and Nipple-Areolar Complex (NAC) Position

Protocol No:
DO607738A

Rev. Date: August, 2018

SIRB ID: 6254

STUDY NAME: CLINICAL EVALUATION OF SAFETY AND EFFICACY OF RADIO-FREQUENCY ASSISTED LIPOLYSIS (RFAL) OF BREAST ENVELOPE AND NIPPLE-AREOLAR COMPLEX (NAC) POSITION

Date: August 2018

Protocol No: D0607738

Revision No.: B

Sponsor: InMode MD Ltd.

[name]
[name]
[name]
[name]
[contact]
[contact]

INMODE

aesthetic solutions

Clinical Evaluation of Safety and Efficacy of Radio-Frequency Assisted Lipolysis (RFAL) of Breast Envelope and Nipple-Areolar Complex (NAC) Position

Protocol No:
DO607738A

Rev. Date: August, 2018

SIRB ID: 6254

APPROVALS:

	Name	Title	Signature	Date
Written by:	[name]	CLINICAL MANAGER		
Edited by:	[name]	VP, RESEARCH AND COMPLIANCE		
Approved by:				

Revision Log:

Revision #	Date	Modification
A		First Release
B	8.8.18	

INMODE
aesthetic solutions

Clinical Evaluation of Safety and Efficacy of Radio-Frequency Assisted Lipolysis (RFAL) of Breast Envelope and Nipple-Areolar Complex (NAC) Position

Protocol No:
D0607738A

Rev. Date: August, 2018

SIRB ID: 6254

PROTOCOL SYNOPSIS

Study Title	CLINICAL EVALUATION OF SAFETY AND EFFICACY OF RADIO-FREQUENCY ASSISTED LIPOLYSIS (RFAL) OF BREAST ENVELOPE AND NIPPLE-AREOLAR COMPLEX (NAC) POSTION
Study Number	D0607738A
Principal Investigators	[name]
Study Design	This is a single center clinical study to determine the safety and efficacy of using Radiofrequency (RF) energy for minimally invasive breast lift procedure. Treatment areas will include breast area.
Study Sites / Country	[name] Maxwell Aesthetics [name]
Planned Study Duration	Study duration including recruitment will be up to 18 months.
Investigational Product	The InMode RF™ platform has been cleared by the United States Food and Drug Administration (FDA) (K151793) for use in dermatological and general surgical procedures for electrocoagulation and hemostasis.
Planned Sample Size	Up to 10 adult subjects

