The InModeRF is a Radio-Frequency device comprising of the following main modules:

- AC/DC power supply isolating system modules from AC voltage
- RF generator providing output of RF power to the hand piece
- Microcontroller controlling RF output, monitoring tissue electrical parameters, skin surface temperature and proper functioning of electronic modules.

InModeRF DEVICE

Hand piece delivers RF power to the subject and has the following main elements

- Internal electrode insulated with Teflon with a treatment tip at the distal end
- External electrode with temperature sensor
- Mechanism adjusting distance between electrodes

[figure not shown]
I N M O D E
aesthetic solutions

Clinical Evaluation of Safety and Efficacy of Radio-Frequency Assisted Lipolysis (RFAL) of Breast Envelope and Nipple-Areolar Complex (NAC) Position

Protocol No:
DO607738A

Rev. Date: August, 2018

SIRB ID: 6254

HAND PIECE

Principles of operation

Operation of InModeRF device is based on the concept of a minimally invasive procedure. The hand piece is comprised of two electrodes where an internal electrode is inserted into subcutaneous fat layer and its size is designed for thermal destruction of adipose tissue with RF energy. A second external electrode is applied to the skin surface. Both electrodes have a rigid connection with an adjustable distance between them. RF power and tip size of the internal electrode are designed to liquefy fat in the vicinity of the electrode tip. The external electrode has a much larger area that creates much lower power density on the skin of the patient. The RF current flows from the internal electrode to the external electrode. The hand piece can monitor both tissue impedance and temperature in real time. The outer temperature measurement acts as safety mechanism that stops the RF current in the case the skin temperature is reaches the desire temperature set by the doctor. The figure below shows RF energy distribution in tissue between electrodes.

[figure not shown]
I N M O D E
aesthetic solutions

Clinical Evaluation of Safety and Efficacy of Radio-Frequency Assisted Lipolysis (RFAL) of Breast Envelope and Nipple-Areolar Complex (NAC) Position

Protocol No:
DO607738A

Rev. Date: August, 2018

SIRB ID: 6254

RF energy distribution between electrodes

STUDY DESIGN

Prospective, self-controlled, open label, single arm clinical study

CLINICAL PROCEDURE

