The risks in this surgical procedure are derived from the physical impact of the surgical treatment on the tissue, the anesthesia used and the biopsy procedure (if applicable and patient's agreement is obtained). The possible risks include pain, excessive skin redness (erythema), damage to natural skin texture (scratching, crusting, blister, burn), bleeding, bruising, infection, scarring, skin contour irregularities and/or asymmetry and pulmonary complications. Certain people may be sensitive to the anesthesia used and therefore require longer time for recovery. Some of the risks of the anesthesia are difficult breathing, redness, itching, and/or swelling at the site of the application or injection. If any of the symptoms occur, tell the study doctor immediately. The biopsy procedure carries the risks of infection and/or scarring.

Should a risk related to the treatment become evident, the physician shall provide the appropriate treatment for this event. Nevertheless, should any sort of damage occur or if the treated areas or the patient in general feel uncomfortable following treatment, the subject should inform the study center for the attention of the study physician.

Subjects will not have to pay for treatment cost that is intended to resolve study complications.

INMODE
aesthetic solutions

Clinical Evaluation of Safety and Efficacy of Radio-Frequency Assisted Lipolysis (RFAL) of Breast Envelope and Nipple-Areolar Complex (NAC) Position

Protocol No:
DO607738A

Rev. Date: August, 2018

SIRB ID: 6254

BENEFITS

Potential benefits may include measurable nipple-areolar lift, as well as improvement in the elongated, tubular appearance in those patients with severe ptosis.

ALTERNATIVES

Besides the traditional surgery for breast tightening, other options include non-invasive skin tightening procedures using lasers, bipolar or monopolar devices as well as ultrasound.

ADVERSE EVENTS

The Physician must document on the Adverse Events form, in standard medical terminology, all adverse signs and symptoms regardless of severity or frequency that are either volunteered by subjects or observed during the course of the study. Included in the description will be the nature of the sign or symptom, the date of onset, whether the event was serious, the severity, the relationship to study treatment or device, the action taken, the date of resolution, and the outcome.

- Possible serious adverse event is any event that:
 - Results in death;

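### The one safety rate the Data Analysis section names rests on an unchecked judgement of relatedness and carries no interval, although events of every cause are collected

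*Combined protocol and SAP*

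**What the plan says.** Data Analysis gives the general method in one sentence: "The data will be analysed by the Sponsor using basic descriptive statistics, as well as comparison tests, where applicable". The next sentence names the only safety rate in the plan: "Treatment-related complications will be monitored and reported; if applicable, their incidence rate will be calculated". That rate is then to be "analysed for any relationship to treatment parameters and/or skin type". The section gives no confidence interval, no denominator (women or breasts), no attribution criteria and no table of events regardless of cause.

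Collection is wider. Under Adverse Events, the Physician documents "all adverse signs and symptoms regardless of severity or frequency", and relationship to the treatment or device is one of the items recorded for each event. The same section sends every serious event to the clinical monitor whether or not it is thought device-related, and has unanticipated events reported to the Sponsor.

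The design is "Prospective, self-controlled, open label, single arm clinical study", the planned size is "Up to 10 adult subjects", and the Synopsis gives the purpose as "to determine the safety and efficacy" of the procedure.

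**The concern.** When a safety rate counts only events judged related, the judgement of relatedness decides the numerator. A control arm would show how often the same events occur without treatment, and an independent assessor would limit the influence of expectation. The protocol provides neither for safety. It does use three independent plastic surgeons to evaluate the photographs (Evaluation section), but describes nothing similar for attribution of adverse events.

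Attribution is also ambiguous here. The Risks section traces harm to the treatment, the anesthesia and an optional biopsy. It lists infection under both the procedure and the biopsy, and redness under both the procedure and the anesthesia. One infection could reasonably be assigned either way, and the assignment would decide whether it enters the named rate.

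The second issue is precision. With so few women, a rate without an interval can suggest a firmer safety finding than the data allow, most of all when the observed count of a serious event type is zero.

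**Working it through.** **The plan's own figure.** There is none to reproduce. The sample size comes with no derivation, and no safety rate, threshold or precision target is stated.

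**Inputs.** At most 10 women (Synopsis). Fewer may be evaluable, because women may withdraw at any time (Discontinuation) and the 12-month visit is optional (Visit 1). Two things are assumed because the documents do not give them: a 95% confidence level, and the woman as the unit of analysis.

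**Effect of attribution.** With n evaluable women and a per-woman rate for one event type, moving a woman's only event of that type from related to unrelated changes the rate by 1/n.

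- n = 10: 1/10 = 10 percentage points, for example from 1/10 (10%) to 0/10 (0%).
- If the woman has another related event of the same type, the rate does not change.
- If the unit were the breast, with 20 breasts, the change would be 1/20 = 5 points. Simple binomial limits would then be unsuitable, because two breasts of one woman are not independent.

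**Exact (Clopper-Pearson) two-sided 95% limits.** For 0/n the upper limit is 1 − 0.025^(1/n). For n = 10 this is 1 − 0.025^0.1 = 1 − 0.6915 = 30.8%. For x events with 0 < x < n, the lower limit is the 2.5% quantile of Beta(x, n − x + 1) and the upper limit is the 97.5% quantile of Beta(x + 1, n − x).

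| Women with the event | Rate | Exact 95% limits |
|---|---|---|
| 0/10 | 0% | 0 to 30.8% |
| 1/10 | 10% | 0.3 to 44.5% |
| 2/10 | 20% | 2.5 to 55.6% |

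**Fewer evaluable women.** The upper limit for 0/n is 33.6% at n = 9, 36.9% at n = 8, 41.0% at n = 7, 45.9% at n = 6 and 52.2% at n = 5.

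**Chance of seeing no event in 10 women.** This is (1 − p)^10, where p is the true risk per woman:

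- p = 5%: 0.95^10 = 59.9%
- p = 10%: 0.90^10 = 34.9%
- p = 20%: 0.80^10 = 10.7%

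An event type with a true risk of one in ten would go unseen in about a third of studies of this size.

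**The case against.** The strongest reply is that the plan excludes nothing. The general sentence on descriptive statistics is unrestricted and could cover every line of the Adverse Events form. A reader might infer that unrelated events are barred from analysis, but the documents do not say so. What they show is that the only rate named is the related one, and that no summary of all events is specified.

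A reader might also infer that relabelling could hide serious harm. The text does not support that. Serious events reach the clinical monitor whatever their attribution, unanticipated events go to the Sponsor with no relatedness condition, and the relationship entry leaves a record for each event. The weakness lies in analysis and reporting, not in collection.

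Three further objections limit the point:

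- The 10-point shift is not a general cost per reclassified event. It needs 10 evaluable women, a per-woman rate, and an event that is the woman's only one of its type.
- A count of 0/10 for any adverse event is unlikely, since pain, redness and bruising are anticipated. Zero is plausible only for specific or serious types.
- Other passages speak of evaluating or documenting safety, and no success rule is stated, so no formal decision is shown to turn on the missing interval.

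The lack of blinding adds little in itself, because one arm leaves no allocation to conceal. The documents also do not say who makes the final attribution used in the analysis.

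These objections narrow the point but do not remove it. The one safety rate the plan commits to still depends on an attribution that nothing in the design checks.

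**Conclusion.** The point holds in limited form. The only safety rate named in Data Analysis is narrower than the data collected, depends on attribution recorded by the Physician without stated criteria, comparator or independent check, and has no interval. The size is 10 percentage points for one woman's sole event of a type, given 10 evaluable women and a per-woman rate. For a specific or serious event type, zero in 10 is compatible with a true risk of up to 30.8%, and zero in 8 with up to 36.9%, at an assumed two-sided 95% level. It would go too far to say that the plan forbids an all-event summary or conceals serious events. The plan leaves such a summary unspecified, and the change is worth making because it relies less on judgement and needs no new data.

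**What to change.** Amend Data Analysis so that the main safety table gives, for each event type, the number and percentage of women with at least one adverse event of that type, regardless of attribution. Each woman is counted once per type, and the number evaluable is shown as the denominator. Present the treatment-related subset as a second table of the same layout. Give exact (Clopper-Pearson) 95% limits with every rate in both tables.

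Counting per woman also settles the unstated unit, which matters because the Treatment Parameters Study section allows different settings on a woman's two sides.

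The cost is one extra table. No new data, visits or subjects are needed, because the Adverse Events form already records all events and their relationship. The headline rate may look slightly less favourable than one restricted to related complications.
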